### 5.10. Secondary Outcomes and Analyses

For Group A and Group A+B in the ARS population, similar to the primary analysis, 2 sets of analysis approaches (copy reference multiple imputation and MMRM) will be used to analyze the change from baseline for the following key secondary endpoints 1 and 2 at Week 26. For endpoint 3, only MMRM analysis will be performed.

- 1) FPG (by laboratory measurement)
- 2) 7-point SMBG
- 3) total daily insulin dose (TDD)

For Group A, the MMRM model will include the following fixed effects: treatment (U-500R CSII, U-500R MDI), weeks on treatment, the interaction between treatment and weeks, and the stratification factors (U-500R at entry versus other insulins, entry HbA1c  $\geq 8.5\%$  or  $< 8.5\%$ ). The model will also include the corresponding baseline of the response variable. For the copy reference approach, the ANCOVA model will include the following fixed effects: treatment (U-500R CSII, U-500R MDI), the stratification factors (U-500R at entry versus other insulins, entry HbA1c  $\geq 8.5\%$  or  $< 8.5\%$ ) and the corresponding baseline measures.

For Group A+B, the same MMRM model and ANCOVA models in Group A above will be used with the addition of the stratification factor (nonusers versus users of GLP-1 receptor agonists or SGLT2 inhibitors).

For SMBG, the average of the 2 non-consecutive-day values for scheduled visits will be used.

Total daily dose will be calculated as the sum of maximum total bolus dose and basal dose at each visit. The maximum total bolus dose of the 3 days prior to each scheduled visit for each subject will be used to calculate the TDD value for data summary and statistical analysis to avoid the underestimated TDD due to missed meal(s). The basal dose will be only collected for 1 day prior to each visit and used to calculate TDD for each visit. Body weight at each visit will be used for TDD (units/kg) calculation. Summary statistics will be done for both actual values and change from baseline (CFBL) values. The percentages of bolus and basal doses from TDD in the U-500R CSII group will be summarized by visit.

Similar to the primary analysis, 2 sets of analysis approaches (repeated-measure [or longitudinal] logistic regression excluding post study treatment discontinuation data and the multiple imputations based logistic regression including post study treatment discontinuation data) will be applied to assess the following secondary objectives in the following values at Week 26:

- proportions of subjects achieving HbA1c targets/values ( $\leq 6.5\%$ ,  $< 7.0\%$ ,  $< 7.5\%$ , and  $< 8.0\%$ )
- proportions of subjects achieving HbA1c targets/values ( $\leq 6.5\%$ ,  $< 7.0\%$ ,  $< 7.5\%$ , and  $< 8.0\%$ ) without documented symptomatic hypoglycemia (SMBG  $< 50$  mg/dL)

The logistic regression model will include similar fixed effects as in the above ANCOVA and MMRM models. The proportion of subjects achieving HbA1c targets with no documented symptomatic hypoglycemia (from baseline to the corresponding visit) will be analyzed using similar logistic regression models including the baseline documented symptomatic hypoglycemia event rate as a covariate.

Analyses to assess the following 2 secondary objectives are presented in Section 5.13 since those are considered safety measures:

- rate and incidence of hypoglycemia (documented [documented symptomatic, asymptomatic, and unspecified], severe, and nocturnal)
- change in body weight between treatment groups and as a function of change in HbA1c

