6.2.2. Other Secondary Objectives

Additional secondary objectives of the study are to compare the efficacy and safety of U-500R given by CSII versus MDI at Week 26 for the main study population Group A and the total study population (Groups A and B) respectively (separately), with respect to the following:

- Proportions of subjects achieving HbA1c targets/values ($\leq 6.5\%$ and $< 8.0\%$).
- Mean change in 7-point self-monitored blood glucose (SMBG) including mean SMBG for each time point measurement.
- Change in TDD (unit and unit/kg).
- Proportions of subjects achieving HbA1c targets/values ($\leq 6.5\%$, $< 7.0\%$, $< 7.5\%$, and $< 8.0\%$) without documented symptomatic hypoglycemia (SMBG < 50 mg/dL).
- Rate and incidence of hypoglycemia (documented [documented symptomatic, asymptomatic, and unspecified], severe, and nocturnal).
- Change in body weight between treatment groups and as a function of change in HbA1c.

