10.4.2. Hypoglycemia

As a secondary objective, the rate/incidence of hypoglycemia will be analyzed and compared between treatment groups. Subjects are encouraged to perform SMBG whenever hypoglycemia may be suspected, either by symptoms experienced or perceived increased risk as related to dietary intake, physical activity, or inadvertent or atypical insulin dosing. All subjects will be instructed to treat a SMBG ≤ 70 mg/dL as hypoglycemia by ingesting 15 gram of CHO (for example, 4 ounces of juice or 3 to 5 gram glucose tabs). All subjects will be advised to contact the site if they experience severe hypoglycemia or SMBG < 50 mg/dL.

Hypoglycemia is defined as ≤ 70 mg/dL (Seaquist et al. 2013) and categorized as follows:

- **Documented hypoglycemia**
 - **Documented symptomatic** – an event that:
 1. is accompanied by signs/symptoms of hypoglycemia, and
 2. is accompanied by a measured SMBG concentration of ≤ 70 mg/dL.
 - **Asymptomatic hypoglycemia** an event that:
 1. is not accompanied with signs/symptoms of hypoglycemia, and
 2. is accompanied with a measured SMBG concentration of ≤ 70 mg/dL.
 - **Unspecified hypoglycemia** an event during that:
 1. no relative signs/symptoms of hypoglycemia are recorded, and
 2. is accompanied with a measured SMBG concentration of ≤ 70 mg/dL.
- **Severe hypoglycemia:** An event accompanied by neuroglycopenic symptoms that result in cognitive impairment such that the patient requires assistance of another person to actively administer CHO, glucagon, or perform other resuscitative actions. During these episodes, the patient has an altered mental status, and cannot assist in their care, is semiconscious or unconscious, or experienced coma with or without seizures, and may require parenteral therapy. Plasma glucose measurements may not be available during such an event, but neurological recovery attributable to the restoration of SMBG concentration to normal is considered sufficient evidence that the event was induced by a low SMBG concentration (≤ 70 mg/dL).
- **Nocturnal hypoglycemia:** Any hypoglycemic event (documented hypoglycemia or severe hypoglycemia) that occurs between bedtime and waking.

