- Edited “Hypoglycemic Analyses” (Section 5.13.2.1) to exclude analyses based on the alternative definition of hypoglycemia with blood glucose <50 mg/dL. The 24-hour analysis by 2-hour interval of the 1-year rates of documented symptomatic and severe hypoglycemia was added.
- In Section 5.8 (Protocol Deviations), the table for the important protocol deviations was updated.

- A new section for the study unblinding plan was added (Section 6).

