##### Documented hypoglycemia:

- **Documented symptomatic hypoglycemia:** an event during which typical symptoms of hypoglycemia are accompanied by SMBG  $\leq 70$  mg/dL.
- **Asymptomatic hypoglycemia:** an event not accompanied by typical symptoms of hypoglycemia but with SMBG  $\leq 70$  mg/dL.
- **Unspecified or unclassifiable hypoglycemia:** an event during which SMBG  $\leq 70$  mg/dL but no information relative to symptoms of hypoglycemia was recorded.
- **Severe hypoglycemia:** an event accompanied by neuroglycopenic symptoms that results in cognitive impairment such that the patient requires assistance of another person to actively administer carbohydrates, glucagon, or perform other resuscitative actions. During these episodes, the patient has an altered mental status, and cannot assist in their care, is semiconscious or unconscious, or experienced coma with or without seizures, and may require parenteral therapy. Plasma glucose measurements may not be available during such an event, but neurological recovery attributable to the restoration of SMBG concentration to normal is considered sufficient evidence that the event was induced by a

low SMBG concentration (SMBG  $\leq 70$  mg/dL). The determination of a hypoglycemic event as an episode of severe hypoglycemia is made by the investigator.

- **Nocturnal hypoglycemia:** any hypoglycemic event (documented hypoglycemia or severe hypoglycemia) that occurs between bedtime and waking.

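### The outcome of reaching an HbA1c target without hypoglycemia does not count a severe hypoglycemic event as a failure

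*SAP*

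**What the plan says.** The outcome is listed in protocol 6.2.2 and 12.2.8 and in SAP 4.2.2 and 5.10, for HbA1c cut points of 6.5%, 7.0%, 7.5% and 8.0%. The SAP 5.10 bullet requires the target to be met "without documented symptomatic hypoglycemia (SMBG $< 50$ mg/dL" (the bracket closes there). Protocol 6.2.2 attaches the same cut to the words "without documented symptomatic hypoglycemia".

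The analysis sentence follows: "The proportion of subjects achieving HbA1c targets with no documented symptomatic hypoglycemia (from baseline to the corresponding visit) will be analyzed". The model is a logistic regression with the baseline rate of documented symptomatic events as a covariate. Neither the event nor the covariate is given a glucose cut in that sentence.

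The general categories are defined elsewhere:

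- **Documented symptomatic.** In SAP 5.13.2 this is "an event during which typical symptoms of hypoglycemia are accompanied by SMBG" at or below 70 mg/dL. Protocol 10.4.2 likewise requires that the event "is accompanied by a measured SMBG concentration of ≤ 70 mg/dL".
- **Severe.** This is defined by altered mental status and the need for another person's help. SAP 5.13.2 says: "Plasma glucose measurements may not be available during such an event". Protocol 10.4.2 says the same.
- **Nocturnal.** SAP 5.13.2 defines this as "any hypoglycemic event (documented hypoglycemia or severe hypoglycemia) that occurs between bedtime and waking", which shows that documented and severe are two separate categories.

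The SAP Revision History records that section 5.13.2.1 was edited "to exclude analyses based on the alternative definition of hypoglycemia with blood glucose <50 mg/dL".

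**The concern.** I found no other planned outcome that combines glycemic benefit with freedom from hypoglycemia in the same subject. It is run for four targets, two populations (Group A and Group A+B) and two analysis approaches, which is 4 x 2 x 2 = 16 analyses. A reader will take a success to mean control reached without a dangerous low.

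The failure rule depends on a glucose value, and the definition of a severe event does not. A subject who needed another person's help, and whose glucose was not measured or was first measured at 60 mg/dL, has no qualifying event and is reported as having reached the target without hypoglycemia. Protocol 10.4.1.1 makes that same event a serious adverse event.

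A smaller gap goes with this. The analysis sentence uses the name of a category whose general definition is 70 mg/dL or below, and it does not repeat the 50 mg/dL cut. A programmer could therefore pick up the wrong flag for the outcome, and has no stated cut for the covariate.

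**Working it through.** The plan gives no expected proportion, power or event count for this outcome, so it has no figure of its own to reproduce. Its only main-trial sizing figure, 240 completers for HbA1c noninferiority, checks out: 2 x (1.96 + 0.84)² x 1.1² / 0.4² gives 119 per arm, 238 in all. 240 / 0.75 = 320 randomized in Group A, or 160 per arm. The point does not depend on the sizing; 320 and 160 serve only as denominators below.

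**Step 1: classify each event type under the written rules.** Assume the HbA1c target is met and the event shown is the subject's only one. Assume also that a severe event with symptoms and a low reading meets the documented symptomatic definition, which is the reading most favorable to the plan.

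| Event | Bullet as written (below 50) | If 70 or below were used | Below 50, or any severe |
|---|---|---|---|
| Severe, no reading | success | success | failure |
| Severe, reading 60 | success | failure | failure |
| Severe, reading 45 | failure | failure | failure |
| Symptomatic, not severe, 60 | success | failure | success |
| Symptomatic, not severe, 45 | failure | failure | failure |
| Asymptomatic, 45 | success | success | success |

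The first two rows are the gap. Moving the cut to 70 mg/dL repairs only the second and also reclassifies the fourth. A severe event with no reading remains a success under either cut, so the gap can be closed only by naming severe events.

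**Step 2: check whether the documents close the gap elsewhere.** They do not. Where the SAP wants both categories it names both: the analysis by 2-hour interval in SAP 5.13.2.1 covers documented symptomatic and severe events together. SAP 5.10 names only the first.

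**Step 3: size.** The trial documents give no severe-event rate for this population. The protocol Introduction cites two figures that serve for scale only.

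- A review of CSII reports: 2 of 55 subjects, 2/55 = 3.6%. In Group A, 320 x 2/55 = 11.6 subjects, or 160 x 2/55 = 5.8 per arm.
- A CSII case series: 0.1 episodes per patient-year, under a different definition of severe. With a constant rate over half a year, 1 - exp(-0.1 x 0.5) = 4.9%, and 160 x 0.0488 = 7.8 per arm.

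Only severe-event subjects who have no symptomatic reading below 50 mg/dL and who also reach the target are affected. Assume 25% to 50% for the first condition and 20% to 40% for the second; neither range is in the documents.

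- Low end: 11.6 x 0.25 x 0.20 = 0.6 subjects per target.
- High end: 11.6 x 0.50 x 0.40 = 2.3 subjects per target.

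Against 320 randomized, that is 0.2% to 0.7%. If every severe-event subject met both conditions, the higher cited rate gives about 8 per arm.

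**The case against.** The best defense is that the 50 mg/dL cut is deliberate. It is attached to this outcome wherever the outcome is listed, in both documents, and the protocol and SAP agree. The analysis sentence comes straight after the bullets and can be read as shorthand for them. This stands. A reader might infer that SAP 5.10 contradicts SAP 5.13.2, but the text fits a narrower cut chosen for one outcome alongside a general definition. The Revision History does not change that: it reports analyses removed from 5.13.2.1 and does not withdraw the cut from 5.10.

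A reader might also infer that the baseline covariate uses the 70 mg/dL category, because SAP 5.5 describes baseline rates for the general categories. SAP 5.10 does not say so. The covariate's cut is unstated, which calls for a clarification and is not a demonstrated mismatch.

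Third, severe events are not hidden. Their incidence and rate are compared between arms for Group A and Group A+B (SAP 5.13.2.1), and all are listed as serious adverse events (SAP 5.13.3). This stands and limits the harm. It does not correct the composite, whose success count would still include subjects with a severe event.

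Finally, the size rests on assumed fractions and on uncontrolled pump series applied to both arms. That is also fair: the figures show an order of magnitude and are not a forecast.

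**Conclusion.** The concern holds in a limited form. As written, the outcome scores a target-achiever with a severe event as a success unless there was also a symptomatic reading below 50 mg/dL. This follows from the definitions and from the absence of any rule for severe events; the SAP does not state it outright. The effect is likely no more than a couple of subjects per target, given the assumed fractions.

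Two stronger conclusions are tempting and unsupported. One is that the rule favors whichever arm has more severe events. That need not follow, since affected subjects must also reach the target and have no other qualifying reading; nor do the documents say that readings are missing more often in the worst events. The other is that the trial's main conclusions are at risk. The outcome is an other secondary objective outside H1 to H10, so the primary test and the familywise error rate are unaffected. The point is worth correcting because the outcome's label would be untrue for the subjects concerned.

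**What to change.** In SAP 4.2.2 and 5.10, and in protocol 6.2.2 and 12.2.8, define failure of the hypoglycemia component as either of the following between baseline and the visit:

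- a documented symptomatic event with SMBG below 50 mg/dL;
- any severe hypoglycemia, whatever the glucose value and whether or not one was recorded.

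In SAP 5.10, add that the 50 mg/dL cut is narrower than the general definition in 5.13.2 and applies to the analysis sentence as well as the bullet. State which cut the baseline-rate covariate uses.

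The cost is one derivation, a few lines of SAP text and a matching change to the protocol's wording of the objective, since the named outcome itself changes. No new data are needed, because severe events are already collected as serious adverse events. Sample size and alpha allocation do not change. Reported success proportions will be slightly lower.

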### 5.11. Exploratory Efficacy Analysis

As mentioned in Section 5.2, exploratory objectives will be analyzed for Group A+B. Summary statistics for both actual values and CFBL values will be reported for each treatment by visit for the following parameters related to 7-point SMBG:

- within-day glucose variability measured by the SD of 7-point SMBG
- between-day glucose variability measured by the SD of the SMBG during the 2-nonconsecutive-day measurement within the same scheduled visit
- within-day and between-day glucose coefficient of variation (CV) of 7-point SMBG (Clarke and Kovatchev 2009)
- average daily risk range (ADRR) defined by (Kovatchev et al. 2006)

- mean of daily differences (MODD) calculated as the average of the difference between values on different days within the same scheduled visit but at the same time

Each of the parameters above will be analyzed using an MMRM model which includes the following fixed effects: treatment (U-500R CSII, U-500R MDI), weeks on treatment, the interaction between treatment and weeks, and the stratification factors (U-500R at entry versus other insulins, entry HbA1c  $\geq 8.5\%$  or  $< 8.5\%$ , and nonusers versus users of GLP-1 receptor agonists or SGLT2 inhibitors). The model will also include the corresponding baseline of the response variable. An ANCOVA will also be used to compare treatment arms at endpoint using the LOCF method. The ANCOVA model will include the same fixed effects in the MMRM model but without the terms involving weeks

The postprandial contribution to total hyperglycemia will be further explored (Riddle et al. 2011). The daily blood glucose (BG) response to meals will be estimated by calculating the incremental AUC of daytime BG from the overall glucose profile. Four areas were calculated geometrically from the seven-point curve as follows:

- 1) normal glycemic exposure ( $AUC_N$ ):  $100 \text{ mg/dL} \times 24 \text{ h} = 2,400 \text{ mg/dL per hour of exposure}$
- 2) basal hyperglycemia (BHG) ( $AUC_B$ ): the area between  $100 \text{ mg/dL}$  and a line projected rightward for 24 hours from the fasting (before breakfast) glucose value in the profile (the area is taken to represent the daily abnormal glycemic exposure resulting from BHG)
- 3) postprandial hyperglycemia (PPHG) ( $AUC_P$ ): the area above the line projected rightward from the fasting sample before breakfast and below the line connecting the 6 remaining points, minus any area below the line projected from the basal value, if applicable (this area is considered a reflection of the postprandial glycemic responses to breakfast, lunch, and dinner)
- 4) total glucose ( $AUC_G$ ): the total area under the glucose curve is the sum of the other 3 areas [ $AUC_G = AUC_N + AUC_B + AUC_P$ ]. As a result, the relative contributions of postprandial and fasting BG to the total BG increment were calculated, respectively, by using the following equations: [ $AUC_P / (AUC_B + AUC_P)$ ] x 100% for the postprandial contribution and [ $AUC_B / (AUC_B + AUC_P)$ ] x 100% for the basal contribution. Negative values were set to zero.

Analyses include Mean (SD) of and Pearson correlation (p-value) between HbA1c CFBL at Week 26 (LOCF) and each of CFBL of:  $AUC_B$ ,  $AUC_P$ ,  $AUC_G$ , BHG contribution and PPHG contribution at Week 26 (LOCF). The  $AUC_B$  and  $AUC_P$  will be analyzed separately by fitting ANCOVA model with baseline corresponding parameter as a covariate, treatment as fixed effect to compare the treatment effect.

Total hyperglycemia (%) separated by BHG and PPHG will be plotted for each treatment in bar chart format with x-axis for different HbA1c category ( $< 6.5\%$ ,  $6.5\%$  to  $< 7\%$ ,  $7\%$  to  $< 7.5\%$ ,  $7.5\%$  to  $< 8\%$ ,  $\geq 8\%$ , and overall).

Proportions of subjects with HbA1c  $\geq 9\%$  or  $< 9\%$  at Week 26 will be reported and will be analyzed using the same logistic regression model used in the analysis of the proportions of subjects achieving different HbA1c targets in Section 5.10.

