7.1.3. Blood Glucose Monitoring

The U-500R dosage will be based on subjects' individual needs, as assessed by SMBG results obtained from monitoring at home. Site personnel may request additional BG monitoring from subjects and/or assess BG values at other times during the study in order to make dose adjustment decisions. Subjects should record both 4- and 7-point SMBG measurements, as well as insulin doses, in the subject diary provided.

7.1.3.1. 4-Point SMBG

Subjects will be instructed to record 4-point SMBGs daily beginning with the screening period. The 4-point SMBG consists of BG measurements at:

- Pre-morning meal (fasting)
- Pre-midday meal
- Pre-evening meal
- Bedtime (at least 2 hours after the evening meal)

7.1.3.2. 7-Point SMBG

All subjects will be instructed to record 7-point SMBG profiles on any 2 nonconsecutive days in the 2 weeks prior to visits as outlined in the study schedule ([Attachment 1](#)); profiles should include weekend day(s), if possible. The timing of the 7-point SMBG measurement over a 24-hour period is as follows:

- Pre-morning meal (fasting)
- 2 hours after the morning meal
- Pre-midday meal
- 2 hours after the midday meal
- Pre-evening meal
- 2 hours after the evening meal
- 0300 hours

7.1.3.3. 0300 Hours SMBG

Subjects will also be instructed to record their 0300 hours BG within 48 hours of each increase in insulin dose titration at telephone and office visits (preferably the first night after the dosage adjustment). The investigator or site personnel will ask the subjects about these BG measurements and the **investigator** will recommend dosage titrations based on glucose targets within the CSII (Section 9.8.1.1) and MDI (Section 9.8.2.1) algorithms during telephone and office visits.

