#### **4.3. Exploratory Objectives**

Exploratory objectives of the study are the following and will be assessed for the total study population (Group A+B):

- The change in patient reported outcomes including Treatment-Related Impact Measure for Diabetes (TRIM-D) and TRIM-D for Diabetes Device (TRIM-DD) surveys from baseline to 26-week value.
- Assess subject-reported OmniPod pump experience via OmniPod U-500 System Exit Questionnaire.
- Assess proportion of subjects with an HbA1c  $\geq 9\%$  and  $< 9\%$  at the 26-week value.
- Postprandial contributions to total glycemic burden at baseline to 26-week values using area under the curve (AUC) analysis of 7-point SMBG profiles.
- Glycemic variability using 7-point SMBG profiles (including within day and day-to-day standard deviation [SD], coefficient of variation, average daily risk range, and mean of daily differences).
- Examine the relationship between gene variants including, but not limited to, insulin receptor, insulin like growth factor-1, melatonin receptor 1B1, adiponectin, transcription factor 7-like 2, phosphoinositide-3-kinase, regulatory subunit 1 and B-cell CLL/lymphoma 11A on clinical outcomes.

- Evaluate subgroups of baseline TDD >2 and ≤2 units/kg, TDD >200 units at baseline that fall below TDD 200 units during the study, baseline TDD >400 and ≤400 units, users of GLP-1 receptor agonists or SGLT2 inhibitors, and geriatric subjects (age ≥65 years and ≥75 years) on each of the primary and secondary objectives.
- Functionality and safe use of the OmniPod U-500 system.

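### On its most literal reading, the between-day glucose SD in SAP 5.11 pools all 14 readings from two profile days and so does not isolate day-to-day variation

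*SAP*

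**What the plan says.** The exploratory objective in SAP 4.3 (matched in Protocol 6.3) concerns glycemic variability from 7-point profiles, "including within day and day-to-day standard deviation [SD], coefficient of variation, average daily risk range, and mean of daily differences". Within-day and day-to-day SD are thus meant to be separate quantities.

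SAP 5.11 turns this into parameters:

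- Within-day: "within-day glucose variability measured by the SD of 7-point SMBG".
- Between-day: "between-day glucose variability measured by the SD of the SMBG during the 2-nonconsecutive-day measurement within the same scheduled visit".
- CV: "within-day and between-day glucose coefficient of variation (CV) of 7-point SMBG", with a literature citation but no formula.
- Mean of daily differences (MODD): "average of the difference between values on different days within the same scheduled visit but at the same time".

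The average daily risk range is listed as well. Each parameter goes into an MMRM comparing CSII with MDI in Groups A and B combined, and into an ANCOVA at the LOCF endpoint.

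On data collection, Protocol 7.1.3.2 states: "All subjects will be instructed to record 7-point SMBG profiles on any 2 nonconsecutive days in the 2 weeks prior to visits". It then lists seven times: before and 2 hours after each of three meals, and 0300 hours. A scheduled visit therefore supplies 2 × 7 = 14 readings.

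**The concern.** The between-day item names neither daily means nor same-time pairs. The MODD item in the same list does state its pairing. Taken literally, the between-day SD is the spread of every reading from both days. Those readings come from before meals, after meals and the middle of the night, so much of their spread is the daily pattern that the within-day SD already measures.

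A between-day statistic should be zero when the two days are identical, and it should not respond to the size of meal excursions alone. If the pooled statistic fails these tests, a difference between arms in it cannot be read as a difference in day-to-day stability. Pump delivery could plausibly change meal excursions, so the two need to be kept apart in this trial.

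**Working it through.** The plan states no figure for this measure, so there is none to reproduce. The check is a variance decomposition.

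**Inputs from the documents.** Two days per visit and seven readings per day (Protocol 7.1.3.2).

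**Inputs that are assumptions.** The documents give no SMBG variance components. Let τ be the SD of the time-of-day profile over the seven times (divisor 7), s_b the SD of a whole-day shift, and s_e the SD of the residual that differs between days at the same clock time. All are in mg/dL.

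**Expected variances.**

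- Pooled 14 readings: (14/13)τ² + (7/13)s_b² + s_e²
- Within one day (7 readings): (7/6)τ² + s_e²
- Two daily means: s_b² + s_e²/7

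**Test 1: identical days.** Take τ = 40 and s_b = s_e = 0. The pooled variance is (14/13) × 1600 = 1723.1, so the SD is 41.5. The SD of the daily means is 0. That the pooled SD is nonzero does not depend on the value chosen for τ, provided it is above 0.

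**Test 2: a range of components.** SDs are square roots of the expected variances.

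| τ / s_b / s_e | Pooled SD | Within-day SD | SD of daily means | Day-shift share of pooled variance |
|---|---|---|---|---|
| 40 / 0 / 0 | 41.5 | 43.2 | 0 | 0% |
| 40 / 0 / 25 | 48.5 | 49.9 | 9.4 | 0% |
| 40 / 20 / 25 | 50.6 | 49.9 | 22.1 | 8.4% |
| 40 / 40 / 25 | 56.7 | 49.9 | 41.1 | 26.8% |
| 20 / 20 / 40 | 47.4 | 45.5 | 25.1 | 9.6% |

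A simulation of 100,000 subjects per row agreed with the three SD columns to within 0.1. For the third row, the pooled variance is 1723.1 + 215.4 + 625 = 2563.5, and its square root is 50.6. Between the second and third rows the day shift rises from 0 to 20. The pooled SD moves by about 4% (48.5 to 50.6), while the SD of daily means more than doubles (9.4 to 22.1).

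**Test 3: two-component range.** Treat the readings within a day as random with SD s_w, and put r = s_b/s_w. The between-day share of the pooled variance is (7/13)r² / [1 + (7/13)r²]:

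| r | 0.25 | 0.5 | 0.75 | 1.0 | 1.5 |
|---|---|---|---|---|---|
| Share | 3.3% | 11.9% | 23.2% | 35.0% | 54.8% |

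**Test 4: what a comparison of arms could show.** Give both arms s_b = 20 and s_e = 25, so their day-to-day variation is the same. Let one arm have τ = 40 and the other a flatter profile with τ = 30. For τ = 30 the pooled variance is (14/13) × 900 + 215.4 + 625 = 1809.6, so the SD is 42.5, against 50.6 for τ = 40. The so-called between-day SD then differs by 8.1 mg/dL, although the SD of daily means is 22.1 in both arms.

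**The case against.** The strongest reply is that the text is under-specified rather than wrong. It does not say that all readings are pooled. The label, set beside a separate within-day item, may point a programmer to daily means or same-time pairs. This is fair, and it is why the point is limited to the most literal reading. It does not remove the need for a change: two programmers could derive different endpoints, and the plainest derivation gives the wrong one. SAP 5.10 does not settle the matter. Its rule, "For SMBG, the average of the 2 non-consecutive-day values for scheduled visits will be used", is written for the secondary SMBG endpoint, and averaging the days removes the very difference that a between-day measure needs.

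The second reply is that the size depends on assumed components. That also stands. At a day-shift SD of 40 in the table above, the pooled and within-day SDs clearly separate (56.7 against 49.9). A reader might infer that the pooled SD is almost entirely within-day variation. That holds only when the day shift is small relative to within-day spread, at a ratio of about 0.5 or less. The residual s_e also complicates the split: it is day-to-day variation at a fixed clock time, yet it enters the within-day SD too.

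The third reply is that MODD, in the same list, compares the two days at matching times and so removes the daily pattern. A reader might infer that the day-to-day objective goes unmeasured; MODD shows that this is not so. One caution applies. The MODD text does not say that differences are absolute. Signed differences would average about zero across subjects, so MODD fills this role only with absolute values.

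Last, a reader might infer that the between-day CV has the same defect. SAP 5.11 gives no formula for it and relies on a cited source that is not part of the documents, so this cannot be established.

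**Conclusion.** The concern holds for the between-day SD read literally. The SD of 14 pooled readings is not a between-day measure: it is nonzero whenever glucose varies over the day, even if the two days match exactly. That conclusion needs no variance estimate. How far it overlaps the within-day SD does depend on assumptions, with a between-day share of variance from about 3% to 55% over ratios of 0.25 to 1.5. At the lower ratios the two SDs would be nearly the same number, and a difference between arms in meal excursions could be reported as one in day-to-day stability.

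The consequence is small. The parameter is exploratory, lies outside the H1 to H10 testing graph in SAP 5.3, and is one of several planned variability measures. No primary or key secondary conclusion depends on it.

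**What to change.** In SAP 5.11, define the between-day SD for each subject and visit as the SD of the two daily mean SMBG values. Define the between-day CV explicitly as that SD divided by the 2-day mean. Keep the same MMRM.

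Do not use the same-time SD averaged over the seven times. The SD of two values is |d|/√2, where d is their difference, so the average is absolute MODD divided by √2 and only rescales a measure already listed. While editing, state that MODD uses absolute differences.

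The cost is a sentence or two in the SAP and one derivation line, using data already collected. The drawback is precision: the SD of two daily means has one degree of freedom per subject-visit. It also carries some residual noise (9.4 mg/dL with no day shift and s_e = 25 in the table above), so comparisons between arms will be noisy and should be read as such.
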